## 6.2 Statistical Methods

We hope to use a simple paired t-test to analyze the data, using volunteers as their own controls.

Crossover study - Each volunteer receives anesthesia 2 times: once without drug (control) and once with caffeine (test). Our animal studies suggest that variance is dramatically minimized when test subjects can be used as their own controls, in this manner. If humans recapitulate the rodent studies then 8 volunteers should provide an adequately

sized sample to answer the research question. The study was originally divided into two parts. The first part, the Pilot study has been completed.

Part 1: In order to demonstrate feasibility and safety, we carried out a pilot study of 2 healthy human volunteers to assess whether caffeine aids these subjects in recovering from isoflurane anesthesia. Recovery times were measured in three ways: as the time between the time when anesthetic is terminated until the subject starts to gag, can open his eyes, and the subject is able to respond to simple commands (like squeeze the clinician's hand). Each of the three endpoints was monitored and plotted separately. In this pilot study caffeine citrate (caffeine) was used at 10 mg/kg. By comparing subjects that wake from anesthesia who are injected with a saline solution to subjects that are injected with caffeine we were able to show that caffeine is as efficient in humans as in rodents. Now that we have demonstrated safety and feasibility, if the IRB gives us permission, we will continue to Part 2 of our study. Time from the end of anesthesia to eye opening will be analyzed, as will be the time from the end of anesthesia to response to a simple command. Each parameter (gagging, eye opening and response to command) will be analyzed and plotted separately.

There are cognitive impairments that last for hours following anesthesia (Nathanson *et al.*, 1995; Larsen *et al.*, 2000; Chen *et al.*, 2001). Reaction times and memory are impaired following anesthesia (Nathanson *et al.*, 1995; Larsen *et al.*, 2000; Chen *et al.*, 2001). Outpatients are being released from surgery/ anesthesia on an ever shortening time scale to save money. It would be significant if clinicians could wake the patients safely, rapidly and completely with no cognitive issues. The psychomotor studies will allow us to assess whether caffeine helps ameliorate the cognitive problems associated with anesthesia. Subjects will be required to carry out a series of simple psychomotor tests thirty minutes after anesthesia and then again two hours later. By comparing results, memory and reaction times we will determine whether Caffeine helps ameliorate cognitive problems, relative to the saline treated controls. Data from each test will be analyzed and plotted separately.

Part 2: Up to 8 additional healthy human males will be recruited for this part of the study. If the effects of caffeine in humans mirror that of the rat, we will need ~8 more volunteers to complete the trial assuming that each volunteer attends all 4 anesthesia sessions. We anticipate some dropout. This is the part we are asking for permission to start.

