study drug (caffeine citrate) or the placebo (saline) will be given intravenously 10 min before the end of 1 hour isoflurane anesthesia. The anesthesiologists will be blinded to the medication injected to the subject since the pharmacists in the IDS GROUP prepare the drug or the placebo control. When isoflurane is turned off, the subject will eliminate isoflurane passively via breathing. We will measure the time between when the isoflurane is stopped to the awakening of the subject. We will record the time to recovery of the gag reflex, until the subject's eyes open, until the subject's mouth opens, and the time until the subject can respond to the command to grip the hand of the attending physician and the removal of the laryngeal mask. After the subject is awake and relatively alert, he will perform psychomotor tests to measure his cognitive function. The subject will be required to complete a simple set of cognitive tests to determine if they are still impaired by anesthetic. Both "control" and test subjects will be required to complete the same tests. In total there are 3 different tests. The tests will be repeated every 15 minutes in order to obtain a recovery time course.

There will be at least two anesthesiologists present during the entire period of anesthesia. Each subject will be given a dose of antiemetic medication, zofran (4 mg) 20 minutes before the end of the anesthesia to minimize the incidence of post anesthesia nausea and vomiting. During the period of anesthesia, we will keep the subject's BP within 20% of its pre-anesthesia value. If the BP falls more than 20% of the baseline, for more than 5 minutes, we will first give IV fluid to replete the fluid deficit due to the restriction of fluid intake prior to the study. Vasoactive medications will be given if necessary.

One hour after the isoflurane is stopped, if the subject is awake, oriented and showing stable vital signs, one of the anesthesiologists may leave the room to prepare for the afternoon session. There will always be at least one anesthesiologist with the test subject at all times. Most of the time there will be two anesthesiologists.

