At the conclusion of the study, we will discharge the subject based on the criteria used in our post anesthesia care unit in the hospitals. In general, the subject should be awake and alert with the stable vital signs. He should be able to drink clear liquid, void and ambulate before discharge home. We will call a car service for him without cost to the subject. The subject will be expected to live within 30 miles of The University of Chicago to make sessions easily accessible. Upon discharge, the subject will be required to be accompanied by a responsible adult. Each session for any given subject will be at least 2 weeks apart. The total time of each session, including the pre-anesthesia preparation, testing and recovery from anesthesia, will be ~4 hours. We will call the subject on the same day and the next day after each session to make sure the subject fully recovers without any adverse event. The subject will get another call a week after the procedure.

Subjects will be tested in this manner a total of two times. In one of the tests they will be anesthetized with isoflurane and injected with a saline solution and in one test they will be anesthetized with isoflurane and then injected with caffeine citrate (15 mg/ kg).

After terminating anesthesia, the subject will perform psychomotor tests to measure his cognitive function. The subject will be required to complete a simple set of cognitive tests to determine if they are still impaired by anesthetic. Both "control" (saline injection) and test subjects (those that obtain caffeine) will be required to complete the same tests.

Memory will be tested with 20 words, after which the subject will be asked to recall the words, order not being important. Two hours later the subject will be asked for the same words. The Digit Symbol Substitution Test asks subjects to substitute symbols for numbers for 60 seconds. Each time there will be different symbol number codes. The subjects will also be asked to estimate a period of time, typically 30 seconds. Blood pressures, heart rate and O2 saturation will be monitored. The entire suite of tests will be repeated two hours later. This latter test will allow us to assess whether the drugs allow recovery of cognitive ability.

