**6. STATISTICAL PLAN AND CONSIDERATIONS**

**6.1 Sample Size Determination**

Members of the IRB should understand that the sample size described above is an estimate, since we could not find good data on human “waking” times from isoflurane anesthesia in the literature. Thus we used our own animal studies to estimate sample size. There are at least three reasons why our sample size might be in error. First, rats are not people. They may get rid of isoflurane differently than do humans due to their higher respiration rates. In addition, rats are genetically more similar to each other than are humans. That would tend to increase human variance relative to that of the rat. On the other hand, the equipment used to anesthetize rats is less sophisticated than that in humans. In humans, the expired anesthetic concentration is measured, thereby allowing for precise anesthetic concentration, in the lungs. This is not possible in rats and so the anesthetic dose applied is less precise. This will tend to lower human variance. This is a long-winded way to say that our sample size estimate may be wrong. In these studies rats were used 4 times (twice with a saline injection twice with an injection of saline containing caffeine), a strategy that reduced variance.

Additional caveats: The 15 mg caffeine citrate that we propose is equivalent to 7.5 mg/kg of pure caffeine. We have never tested 7.5 mg/kg caffeine in rats, nor have we ever studied isoflurane at a concentration of 1 MAC.

We use the following stringent criteria to determine sample size: Power will be set to 95% and  $p \leq 0.01$ .

Rats waking from isoflurane anesthesia with 5 mg/kg caffeine (isoflurane ~ 1.5 MAC):  
(Control - saline injection) - Mean = 540 sec, SD = 159.04  
(Test - 5 mg/kg caffeine in saline injection) - Mean = 269.67 sec, SD = 103.69  
At this concentration of caffeine we would need  $n=12$  measurements for control and  $n=12$  measurements for caffeine to meet our stated stringent criteria. If each person were used for one control and one caffeine measurements we would need 12 people for the study.

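### Section 6.2 promises a yes/no answer on cognition from at least six separate comparisons, but names no deciding test, time point, significance level or adjustment

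*Combined protocol and SAP*

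**What the plan says.** On cognition, section 6.2 states the aim as a determination: "we will determine whether Caffeine helps ameliorate cognitive problems, relative to the saline treated controls". The analysis rule that follows is "Data from each test will be analyzed and plotted separately".

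The number of tests comes from section 5.2: "In total there are 3 different tests". It describes word recall, the Digit Symbol Substitution Test and estimation of a time interval. The sentence in 6.2 that states the aim refers to memory and reaction times, yet 5.2 describes no reaction-time test under that name.

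The timing is given in two ways.
- Section 6.2: "Subjects will be required to carry out a series of simple psychomotor tests thirty minutes after anesthesia and then again two hours later". Section 5.2 agrees in one place: "The entire suite of tests will be repeated two hours later".
- Elsewhere section 5.2 says: "The tests will be repeated every 15 minutes in order to obtain a recovery time course".

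Section 6.2 names a paired t-test. Section 6.3 adds that all data are analysed twice: a paired t-test on subjects who complete both sessions, and an unpaired t-test on all data. Section 9.1 mentions a t-test without further detail. None of these sections gives a significance level or sidedness.

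The one level in the plan, p at or below 0.01 with 95% power, is in section 6.1 under the words "We use the following stringent criteria to determine sample size". It is applied there to rat waking times.

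**The concern.** A yes/no question needs a rule that turns results into an answer. Here at least six comparisons bear on one question, and the plan does not say which of them decides it, or how many must agree. After unblinding, the team could in good faith present whichever test and time looks best as the answer, and a reader could not tell whether that choice was made beforehand. Section 14 commits to publishing the psychomotor results, so a statement about cognition is likely to appear in print. The 0.01 criterion may also reassure a reader about this claim, although nothing carries it from the sample-size section into the analysis.

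**Working it through.** **1. The plan's own use of 0.01.** Section 6.1 gives rat waking times of 540 s (SD 159.04) and 269.67 s (SD 103.69). The difference is 270.33 s and the pooled SD is √((159.04² + 103.69²)/2) = 134.25 s. A two-sample t-test at two-sided 0.01 with 95% power needs 11 per condition (power 95.9%); the stated 12 gives 97.6%. The 0.01 is therefore the input to a waking-time sample size, and that figure is reproduced to within one. Nothing in the calculation concerns the cognitive tests.

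**2. Number of comparisons.** 3 tests (5.2) × 2 times (6.2) = 6. With both analyses in 6.3, 6 × 2 = 12 p-values. Six is a lower bound, because no method in the plan pools the two times and the 15-minute schedule would add more.

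**3. Independent comparisons, no true effect.** P(at least one significant) = 1 − (1 − α)^6.
- α = 0.05: 1 − 0.95^6 = 26.5%. In caffeine's favour only: 1 − 0.975^6 = 14.1%.
- α = 0.01: 1 − 0.99^6 = 5.9%. In favour only: 1 − 0.995^6 = 3.0%.

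**4. Correlated comparisons.** The same men repeat the same tests, so the differences will be correlated. The documents give no correlation, so a range is assumed. Null trials of 8 pairs were simulated with six equally correlated normal differences, each tested by a two-sided paired t-test on 7 degrees of freedom (critical values 2.36 and 3.50).

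| Correlation | Any, 0.05 | In favour, 0.05 | Any, 0.01 | In favour, 0.01 |
|---|---|---|---|---|
| 0 | 26% | 14% | 5.9% | 3.1% |
| 0.3 | 25% | 13% | 5.6% | 2.8% |
| 0.5 | 22% | 11% | 5.4% | 2.7% |
| 0.7 | 18% | 9% | 4.5% | 2.3% |
| 0.9 | 12% | 6% | 3.0% | 1.5% |

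**5. Allowing either the paired or the unpaired result to count.** With complete data on 8 men, six outcomes, and assumed correlations of 0 to 0.5 both between outcomes and within subject, the chance of at least one significant result is 22-34% at 0.05 and 5-9% at 0.01.

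**6. What a level alone would do.** Stating 0.01 for each of six comparisons still leaves 3-6% overall. To hold the whole family at 0.05 by Bonferroni, each comparison would need 0.05/6 = 0.0083; to hold it at 0.01, 0.01/6 = 0.0017. Naming one deciding comparison makes the error rate of the claim equal to the stated level, with no adjustment.

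**The case against.** The case on the other side has four parts.

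- **A single positive test is not said to be enough.** A reader might infer from 6.2 that any one significant result will support the cognitive claim. The documents do not say so. Separate analysis and plotting may also mean description only. This stands: the supportable statement is that no decision rule is given. But the plan never calls these analyses exploratory, and its verb is to determine.
- **The level of 0.05 is not in the plan.** A reader might assume that convention, or might equally carry 0.01 over from 6.1. This stands, so both are shown. At 0.01 the excess is modest.
- **The 15-minute schedule should not be multiplied into tests.** Nine times over an assumed two hours would give 27 comparisons, and 1 − 0.95^27 = 75% if all were independent. The documents give no length for that schedule and describe it as a recovery curve, without saying that each point is tested. Independence of 15-minute repeats in one man is implausible; at correlation 0.9 the figure is about 20%. That larger number is not relied on here.
- **Cognition is secondary.** The study summary and sections 1.2, 2.8 and 14 place it there, and section 2.7 describes the goal as emergence. Section 7.2 does set cognition beside emergence as a goal, but the endpoint hierarchy governs. This stands and limits the importance of the point.

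**Conclusion.** The gap is real and moderate in size. The plan undertakes to answer a question about cognition and leaves open which test, which time, which of two analyses and which level gives the answer. On six paired comparisons with 8 pairs and no effect, the chance of at least one significant result is about 12-26% at an assumed 0.05 (6-14% in caffeine's favour) and about 3-6% at 0.01 (1.5-3% in favour). These figures assume normal differences, no dropout, and correlations between 0.9 and 0 that the documents do not supply. They measure the opportunity for a chance finding; they do not show that the team intends to claim on one. The emergence endpoints are not touched by this point.

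**What to change.** In section 6.2, before the code is broken:

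1. State the two-sided significance level for the cognitive comparison.
2. Name one lead cognitive measure at one time, analysed by the paired t-test. The Digit Symbol score at the thirty-minute battery is one example; the sponsor may prefer another.
3. Base any cognitive claim on that comparison alone.
4. Report all other cognitive tests and times, and the unpaired analysis, as exploratory, with confidence intervals and no claim.
5. Reconcile the two-battery schedule in 6.2 and 5.2 with the 15-minute schedule in 5.2, and the reference to reaction times with the tests that 5.2 describes.

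The change is a short paragraph plus the schedule correction. The price is that an isolated effect on another test or time could be described but not claimed.

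The level deserves thought. With 8 pairs and an assumed standardised paired difference of 1.0, the noncentrality is 1.0 × √8 = 2.83. The power of one paired t-test is then about 35% at two-sided 0.01 and 68% at 0.05. For that reason I would not also make the cognitive test conditional on a sequence of emergence tests at 0.01. Such a sequence would also need a settled first step, and the study summary (gag reflex) and section 2.7 (eye opening) disagree on the primary endpoint.

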We are using human volunteers twice, not four times like the rat population, we expect higher variance. Nonetheless, we expect 8 total volunteers will satisfy our study. This is because we are using a higher concentration of caffeine (7.5 mg/kg), which should produce a larger response than the 5 mg/kg shown above, and we will employ a lower concentration of isoflurane (1 MAC), which should be easier to antagonize.

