### **6.3 Subject Population(s) for Analysis**

The data from all subjects will be analyzed without knowledge of whether the data comes from a control or test condition. After breaking the code, data will be grouped accordingly. All data will be analyzed in two different ways. Using a paired t-test data from subjects that have completed the two anesthesia sessions of the study will be analyzed and plotted. Separately, using an unpaired t-test all data will be grouped together including that from subjects who did not finish the trial. In this way the data will be compared. Only data from subjects that failed the toxicology screen will be excluded.

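### Section 6.2 makes about 8 volunteers conditional on four anesthesia sessions each, but the design has two; the 95% power at p ≤ 0.01 is worked out for 12 people and not shown for 8

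*Combined protocol and SAP*

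**What the plan says.** Section 6.1 sets the criterion for sample size at 95% power with p ≤ 0.01. From the rat experiment at 5 mg/kg it obtains 12 control and 12 caffeine measurements, and it translates this to the crossover: "If each person were used for one control and one caffeine measurements we would need 12 people for the study". It then notes that humans are used twice where the rats were used four times, expects higher variance for that reason, and continues: "Nonetheless, we expect 8 total volunteers will satisfy our study". The reasons given are a higher caffeine dose and a lower isoflurane concentration. Section 6.2 adds that using subjects as their own controls reduces variance. Section 6.1 is open about its limits: "This is a long-winded way to say that our sample size estimate may be wrong".

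The Part 2 paragraph of section 6.2 supports the same number differently: "we will need ~8 more volunteers to complete the trial assuming that each volunteer attends all 4 anesthesia sessions".

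Everywhere else the number of anesthesias is two. Section 5.2 says "Subjects will be tested in this manner a total of two times", and section 6.3 defines the main analysis the same way: "Using a paired t-test data from subjects that have completed the two anesthesia sessions of the study will be analyzed and plotted". Sections 2.3 and 2.5, the schema after section 5.2 and the crossover paragraph of 6.2 agree. Section 2.2 requires 6 to 8 completers. The opening line of section 5 counts four sessions in all, where section 2.3 counts three (one screening, two anesthesia).

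**The concern.** Two linked points. First, the four-session sentence is current text in the request to start Part 2, and the session count bears on N. If four sessions meant two saline and two caffeine, as in the rats, 8 people would supply more measurements per condition than section 6.1 requires. With the actual two sessions they supply fewer.

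Second, the only calculation tied to the plan's power criterion gives 12 people for the design that will be run. The step down to 8 has no number behind it in section 6. A reader, including an IRB deciding whether to expose healthy men to general anesthesia, could take the 95% criterion to describe a trial of 8, or of 6 completers. If the trial then gave a null result, nobody could say what size of effect it had been able to detect.

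**Working it through.** **Session count.** Required by section 6.1: 12 measurements per condition.

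- Four sessions, two per condition: 8 × 2 = 16 per condition, above 12.
- Two sessions, one per condition: 8 × 1 = 8 per condition, below 12.

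**Inputs from the documents.** Control 540 s, SD 159.04; caffeine 5 mg/kg 269.67 s, SD 103.69; alpha 0.01; power 95% (all section 6.1). Largest rat reduction in waking time about 60.5% (section 1.1.3, Fig. 2). Paired t-test (section 6.2).

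**Assumptions, because the documents give no figure.** Within-subject correlation ρ of 0, 0.25 and 0.5. Sidedness is not stated, so both are shown. Rat SDs are held fixed.

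**Effects.** 540 − 269.67 = 270.33 s, which is 50.1% of 540. Largest rat effect: 0.605 × 540 = 326.7 s.

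**Reproducing the plan's 12.** Pooled SD = √((159.04² + 103.69²)/2) = 134.25, and 270.33/134.25 = 2.01. A two-sided unpaired t-test (noncentral t) needs 11 per condition for 95% power and has 97.6% at 12. A two-sided paired t-test with ρ = 0 has 94.3% at 12 and needs 13. The plan's 12 is therefore reproduced approximately, by a calculation that takes little or no credit for pairing.

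**Power at 8 and 6.** SD of the paired difference = √(159.04² + 103.69² − 2ρ × 159.04 × 103.69), which is 189.9, 166.7 and 139.8 s at ρ = 0, 0.25 and 0.5. The noncentrality is the effect × √N divided by that SD. For N = 8, effect 270.33 and ρ = 0 it is 270.33 × √8/189.9 = 4.03, against a two-sided critical value of 3.50 on 7 degrees of freedom, giving 68.8%.

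| N | Effect | Sides | ρ = 0 | ρ = 0.25 | ρ = 0.5 | ρ needed for 95% |
|---|---|---|---|---|---|---|
| 8 | 270.33 s | two | 68.8% | 81.4% | 93.6% | 0.54 |
| 8 | 270.33 s | one | 81.4% | 90.7% | 97.7% | 0.39 |
| 8 | 326.7 s | two | 86.3% | 94.2% | 99.0% | 0.28 |
| 8 | 326.7 s | one | 93.8% | 98.0% | 99.8% | 0.06 |
| 6 | 270.33 s | two | 42.4% | 54.5% | 72.0% | 0.78 |
| 6 | 270.33 s | one | 58.7% | 70.9% | 85.6% | 0.67 |
| 6 | 326.7 s | two | 60.4% | 73.3% | 87.9% | 0.64 |
| 6 | 326.7 s | one | 76.2% | 86.5% | 95.6% | 0.48 |

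**Smallest paired N for 95% power** at ρ = 0, 0.25, 0.5:

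- 270.33 s: 13, 11, 9 two-sided; 11, 9, 8 one-sided.
- 326.7 s: 10, 9, 7 two-sided; 9, 8, 6 one-sided.

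**The case against.** The four-session phrase looks like a leftover with no operational effect. No dose, visit or analysis depends on it, and section 6.1 argues for 8 while stating plainly that humans are used twice. That is right about conduct, and exposure per subject is not in doubt. It remains a wrong figure in current text that justifies N.

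The plan never claims in so many words that 8 people give 95% power. It attaches the figure to 12, departs from it openly, gives reasons and warns that the estimate may be wrong. This also stands, and it limits the finding to something not demonstrated. But the warning explains why rat data may mislead; it does not say what power 8 gives.

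The correlations are assumptions, and the 12 ignores most of the benefit of pairing on which section 6.2 relies. At the larger effect the caffeine SD might also shrink with its mean: if it scaled to about 82 s (103.69 × 213.3/269.67), two-sided power at 8 would be 90%, 96% and 99%, and the correlation needed would fall from 0.28 to 0.20. That would help the case for 8. On the other side, section 6.1 itself expects higher variance in humans than in the rats.

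The pilot figures in section 1.1.4 are not legible in the public copy, so they may have informed the choice of 8. Section 6 does not draw on them for a power figure. Finally, section 2.2 allows the IRB to be asked for more subjects after dropout, which softens the case of 6 completers without removing it.

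**Conclusion.** The concern holds. The four-session condition in section 6.2 is wrong: the design has two, giving 8 measurements per condition at N = 8 and not the 16 that four sessions would give, against the 12 the plan requires. The 95% power at p ≤ 0.01 is supported by the plan's calculation for 12 people and not shown for 8.

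On the plan's rat inputs, two-sided power at 8 runs from 69% to 94% at the 5 mg/kg effect and from 86% to 99% at the largest rat effect; at 6 completers and the 5 mg/kg effect it is 42% to 72%. These figures rest on assumed correlations of 0 to 0.5, rat SDs carried over to humans, and an upper effect that is the rat maximum over doses up to 25 mg/kg and does not quantify the lighter isoflurane. This does not show that 8 is too few. Eight meets the criterion under some reasonable assumptions and misses it under others, and the plan does not say which it makes.

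**What to change.** - In the Part 2 paragraph of section 6.2, replace four anesthesia sessions with two. Make this change together with the power statement below; otherwise the sentence would still assert about 8 volunteers without support.
- In the opening line of section 5, change the visit count from four to three, to agree with section 2.3.
- In sections 6.1 and 6.2, say that 95% power at p ≤ 0.01 belongs to the 12-person calculation, and state whether the test is one- or two-sided.
- Say that power at 8 or 6 completers depends on the within-subject correlation, the sidedness and the assumed effect, and give the range. For 8 and correlations of 0 to 0.5: about 69% to 94% two-sided or 81% to 98% one-sided at the 50% effect, and 86% to 99% two-sided at the 60.5% effect. If the team has its own basis for a correlation or a human effect, it should name it and use that.

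The cost is wording in sections 5, 6.1 and 6.2, with no extra subjects, visits or doses. The price is that the power a reader attributes to the trial becomes conditional and, under several assumptions, lower than 95%.
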